## **15.0 RESEARCH PARTICIPANT REGISTRATION AND RANDOMIZATION PROCEDURES**

### **15.1 Research Participant Registration**

Confirm eligibility as defined in the section entitled Criteria for Patient/Subject Eligibility.

Obtain informed consent, by following procedures defined in section entitled Informed Consent Procedures.

During the registration process registering individuals will be required to complete a protocol specific Eligibility Checklist.

All participants must be registered through the Protocol Participant Registration (PPR) Office at Memorial Sloan-Kettering Cancer Center. PPR is available Monday through Friday from 8:30am – 5:30pm at [contact]. The PPR fax numbers are [contact] and [contact]. Registrations can be phoned in or faxed. The completed signature page of the written consent/verbal script and a completed Eligibility Checklist must be faxed to PPR.

### **15.2 Randomization**

Randomization will be performed using the Clinical Research Database (CRDB), the central computing facility for clinical research at MSKCC. This system will generate a treatment assignment using the method of permuted blocks, at the time the patient is registered. Due to the nature of the treatment, the interventional radiologist may not be blinded but the radiologists assessing response to treatment will be blinded to treatment assignment.

## **16.0 DATA MANAGEMENT ISSUES**

A Research Study Assistant (RSA) will be assigned to the study. The responsibilities of the RSA include project compliance, data collection, abstraction and entry, data reporting, regulatory monitoring, problem resolution and prioritization, and coordination of the activities of the protocol study team.

The data collected for this study will be entered into a secure database. Source documentation will be available to support the computerized patient record.

### **16.1 Quality Assurance**

Quarterly registration reports will be generated to monitor patient accruals and completeness of registration data. Routine data quality reports will be generated to assess missing data and inconsistencies. Accrual rates and extent and accuracy of evaluations and follow-up will be monitored periodically throughout the study period and potential problems will be brought to the attention of the study team for discussion and action

Random-sample data quality and protocol compliance audits will be conducted by the study team, at a minimum of two times per year, more frequently if indicated.

### **16.2 Data and Safety Monitoring**

The Data and Safety Monitoring (DSM) Plans at Memorial Sloan-Kettering Cancer Center were approved by the National Cancer Institute in March 2007. The plans address the new policies set forth by the NCI in the document entitled "Policy of the National Cancer Institute for Data and Safety Monitoring of Clinical Trials" which can be found at:

<http://cancertrials.nci.nih.gov/researchers/dsm/index.html>. The DSM Plans at MSKCC were established and are monitored by the Office of Clinical Research. The MSKCC Data and Safety Monitoring Plans can be found on the MSKCC Intranet at:

<http://mskweb2.mskcc.org/irb/index.htm>

There are several different mechanisms by which clinical trials are monitored for data, safety and quality. There are institutional processes in place for quality assurance (e.g., protocol monitoring, compliance and data verification audits, therapeutic response, and staff education on clinical research QA) and departmental procedures for quality control, plus there are two institutional committees that are responsible for monitoring the activities of our clinical trials programs. The committees: *Data and Safety Monitoring Committee (DSMC)* for Phase I and II clinical trials, and the *Data and Safety Monitoring Board (DSMB)* for Phase III clinical trials, report to the Center's Research Council and Institutional Review Board.

During the protocol development and review process, each protocol will be assessed for its level of risk and degree of monitoring required. Every type of protocol (e.g., NIH sponsored, in-house sponsored, industrial sponsored, NCI cooperative group, etc.) will be addressed and the monitoring procedures will be established at the time of protocol activation

## 17.0 PROTECTION OF HUMAN SUBJECTS

All the patients will sign informed consents and will have all their questions fully addressed before enrolling the study. By definition patients will not be surgical candidates, however alternative options for treatment such as conventional embolization outside the study, will be discussed thoroughly, as well as the risks and benefits of embolization. Although only the usual risks of hepatic artery embolization are expected in both groups, study patients will be carefully monitored for unusual or unanticipated events. Cardiac function will be evaluated in the LC Bead group to look for doxorubicin related cardiotoxicity. All the data will be confidential, maintained in a password protected electronic database and will comply with all HIPAA guidelines.

### 17.1 Privacy

MSKCC Privacy Office may allow the use and disclosure of protected health information pursuant to a completed and signed Research Authorization form. The use and disclosure of protected health information will be limited to the individuals described in the Research Authorization form. A Research Authorization form must be completed by the Principal Investigator and approved by the IRB and Privacy Board.

### 17.2 Serious Adverse Event (SAE) Reporting

An SAE is defined as a grade 3 or 4 adverse event using the Common Terminology Criteria for Adverse Events (CTCAE) 3.0. For the purpose of this study, an unanticipated device effect (UADE) will mean any event that is rarely observed after hepatic arterial embolization, rarely seen in patients hospitalized with diagnosis of cancer or patients receiving doxorubicin.

Any SAE must be reported to the IRB/PB as soon as possible but no later than 5 calendar days. The IRB/PB requires a Clinical Research Database (CRDB) SAE report be submitted electronically to the SAE Office at [[contact]](mailto:[contact]) containing the following information:

#### Fields Populated from the CRDB:

- Subject's name (generate the report with only initials if it will be sent outside of MSKCC)
- Medical record number
- Disease/histology (if applicable)
- Protocol number and title

#### Data Needing to be Entered:

- The date the adverse event occurred
- The adverse event
- Relationship of the adverse event to the treatment (drug, device, or intervention)
- If the AE was expected
- The severity of the AE
- The intervention
- Detailed text that includes the following information:
  - A explanation of how the AE was handled
  - A description of the subject's condition

- Indication if the subject remains on the study
- If an amendment will need to be made to the protocol and/or consent form

The PI's signature and the date it was signed are required on the completed report.

For IND/IDE protocols:

Only UADEs and patient deaths will be reported to the FDA as they occur. For these reports, The CRDB AE report should be completed as above and the FDA assigned IND/IDE number written at the top of the report. If appropriate, the report will be forwarded to the FDA by the SAE staff through the IND Office. **All other SAEs will be recorded as part of the study's data and will be included in the study's progress reports to the FDA.**

This study will collect all SAEs that occur from date of consent until the patient is off study. Since elevation in liver function tests is expected in the immediate post treatment period, no elevation in liver function tests occurring within 2 weeks following treatment will be reported as an SAE, although all elevations will be recorded and captured among the data for the study. The following is a list of the liver function tests: Alkaline Phosphatase, ALT, AST, and Bilirubin. All other elevations to Grade 3 or 4, along with any hospitalization will be reported as SAEs and only reported to the FDA as they occur if considered an UADE.

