## **Day 1**

All patients will have a CBC drawn the day after embolization.

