## **Time 0 + 10-14 days**

Patients will have a CBC drawn 10-14 days after embolization. This may be done locally.

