## **Time 0 + 2-3 weeks**

Patients will be seen in clinic within 2-3 weeks of complete treatment (Time 0). They will have vital signs (weight, blood pressure, temperature, and heart rate), CBC, chemistry profile with liver function tests, coagulation studies, AFP level, and evaluation of any treatment toxicity. The patients will also have a triple phase CT scan. This is the CT scan that will be used to determine response to treatment

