## **11.0 TOXICITIES/SIDE EFFECTS**

Following embolization 80% of patients experience some degree of post-embolization syndrome consisting of pain, fever, nausea and/or vomiting for which they receive supportive care. Liver abscess is a recognized complication, but is typically seen only in patients who have had a bilio-enteric bypass, or for some other reason do not have an intact sphincter of Oddi. Liver abscesses are usually managed with antibiotics and catheter drainage rarely is surgical debridement necessary. Post embolization cholecystitis is occasionally seen, presumably from inadvertent embolization of the cystic artery, although this usually resolves without treatment pain and nausea/vomiting may prolong hospital stay. Very rarely more severe consequences of non-target embolization are seen, such as pancreatitis or gastric or duodenal ulceration. Transient deterioration in liver function or even frank liver failure may occur, more commonly following embolization of more than 75% of the liver volume, or in patients with marginal underlying hepatic function. Cutaneous manifestation of embolization may be seen when non-hepatic vessels such as the right phrenic or internal mammary arteries are embolized when they provide collateral flow to hepatic tumors. These cutaneous findings are usually asymptomatic and resolve without treatment. Very rarely death has occurred from pulmonary embolization when particles pass through arterial-systemic venous shunts into the pulmonary artery branches. There is no known treatment for this complication.

Cardiac toxicity is a risk when doxorubicin is administered systemically. Given the affinity of doxorubicin for LC Bead, results of previous clinical, and the favorable AUC curve for doxorubicin eluting LC Bead it is possible, but unlikely, that cardiac toxicity might occur.

Reproductive risks: Patients should not become pregnant or father a baby while on this study because the drugs and radiation used in this study can affect an unborn baby.

[figure not shown]
Toxicity will be graded according to the NCI Common Terminology Criteria for Adverse Events (CTCAE) 3.0.

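### Section 17.2 relies on recording all early liver-test rises, but no liver test is scheduled between completed treatment and the 2-3 week visit, apart from one extra panel around the second session in two-session patients

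*Combined protocol and SAP*

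**What the plan says.** Section 17.2 sets the reporting rule: liver-test rises in the 2 weeks after treatment are not filed as SAEs, "although all elevations will be recorded and captured among the data for the study". It then defines the scope: "The following is a list of the liver function tests: Alkaline Phosphatase, ALT, AST, and Bilirubin".

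The Section 10.0 text gives the laboratory schedule after embolization. For Day 1: "All patients will have a CBC drawn the day after embolization". For days 10-14: "Patients will have a CBC drawn 10-14 days after embolization. This may be done locally". Neither entry mentions a liver test. Liver function tests first appear at the visit 2-3 weeks after Time 0, which footnote 3 of the schedule table defines as the day treatment is completed, whether in one session or two. The post-procedure care text in Section 9.0 names no liver test.

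There is one exception. Section 9.0 (on patients needing a second embolization) and footnote 2 of the table give two-session patients an additional clinic visit, with liver function tests, within 2 weeks of the second embolization.

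Section 2.0 makes toxicity in each arm a secondary objective. Section 11.0 says it will be graded by CTCAE 3.0.

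**The concern.** Section 17.2 takes early liver-test rises out of SAE reporting and relies on the study data to hold them instead. For these rises the recorded data are the only route, so it matters whether the schedule fills it.

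Liver injury is a recognized risk of embolization in both arms. Section 11.0 warns: "Transient deterioration in liver function or even frank liver failure may occur". Section 3.0 says the study should help judge whether the possible side effects of adding chemotherapy justify further work. Because Section 17.2 expects some rise after treatment in any case, an informative comparison of the arms rests on how high and how frequent the rises are, and that requires values from all patients. If values exist only for patients whom someone chose to test, a table of worst grade by arm has no defined denominator, and peaks that resolve before the 2-3 week visit are lost.

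**Working it through.** No sample size, power or event count enters this point, and the plan gives no figure to reproduce. The check sets the reporting rule beside the schedule and works out the visit windows.

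**1. Period covered by Section 17.2.** 2 weeks = 14 days after treatment. The safety endpoint in Section 1.0 covers 30 days after a procedure, so the exemption covers up to 14/30 = 47% of that period for these four tests.

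**2. Single-session patients.** Counting from Time 0:

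| Scheduled contact | Day | CBC | Liver tests |
|---|---|---|---|
| Day 1 | 1 | yes | no |
| 10-14 days | 10-14 | yes | no |
| 2-3 week visit | 14-21 | yes | yes |

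In days 1-13 there are 2 scheduled CBCs (the second if drawn by day 13) and 0 scheduled liver panels. The 2-3 week visit meets the 14-day period only if it is held on day 14 exactly.

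**3. Two-session patients.** Let S be the day of the second session, counted from the first. Section 9.0 gives S = 14 to 42. Let V be the day of the extra visit. The text does not say whether V precedes or follows S.

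- *V before S*, as the column's position ahead of Time 0 suggests: V lies between S - 14 and S.
  - Over all S this gives 14 - 14 = day 0 to day 42 after the first session.
  - V can fall within 14 days of the first session only if S - 14 ≤ 14, that is S ≤ 28.
  - V must fall within 14 days only if S = 14.
  - Nothing then covers the period from Time 0 to the 2-3 week visit.
- *V after S*: V lies on days 0-14 after Time 0, so the second session is covered once. Counted from the first session, V lies between S and S + 14, so it is day 14 at the earliest and the first session has no panel inside its own 2 weeks, except at that boundary.

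On either reading there is one scheduled panel between an embolization and the 2-3 week visit, and the 2 weeks after each session are not both reliably covered.

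**4. Table marks.** In the schedule table as reproduced, the two liver-test rows have a mark in the Within 2 weeks and Time 0 columns and none in the Within 4 weeks column. Section 8.0 places the baseline liver tests within 4 weeks of the first embolization. The first two marks therefore look shifted one column to the right, in the source or in the extracted text. The finding does not depend on this: shifted or not, the Day 1 and 10-14 day cells are empty in these rows, and the Section 10.0 text agrees.

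**5. Who might order unscheduled tests.** Section 4.1 says the operating radiologist will know the arm. Section 14.0 says this radiologist will not be blinded, while Sections 1.0 and 15.2 say only that this is possible. Blinding is stated for image and data analysts and for CT readers. Nothing says who orders interim blood tests or whether they know the arm.

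**The case against.** The strongest reply is that Section 17.2 is only a recording rule. Expected early rises are not filed as SAEs, and any that happen to be found are kept. It does not commit the study to drawing blood on set days, so there is no formal contradiction with Section 10.0. That reading is fair, but it does not remove the gap. If the plan is followed as written, the early liver-toxicity data still come only from the patients someone tested.

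A second reply is that the effect on endpoints is limited. This stands. The safety endpoint is the SAE rate within 30 days, and Section 17.2 keeps these rises out of SAE reporting. Any hospitalization is reported as an SAE, so a liver event leading to admission has its own route. Both arms also have a liver panel and toxicity evaluation at 2-3 weeks, inside the 30 days. What is lost is the height and frequency of early rises for the toxicity objective.

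A reader might infer that no patient has any liver test between an embolization and the 2-3 week visit. The extra visit for two-session patients rules that out. A reader might also infer that staff who know the arm test the arms differently. The documents do not support that either: only the operating radiologist is described as knowing, or possibly knowing, the arm, and the ordering of interim tests is not described. The size of any such bias cannot be derived.

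It is also fair to say that the plan nowhere states that a CBC sample can be used for a chemistry panel, so an extra tube may be needed.

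**Conclusion.** The point holds in limited form. After completed treatment, single-session patients have 0 scheduled liver panels before the 2-3 week visit. Two-session patients have one extra panel, tied to the second session, which does not reliably cover the 2 weeks after each session. Capture of early rises in the four named tests therefore depends on unscheduled testing, and the early part of the toxicity-by-arm comparison has no defined denominator.

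Differential testing by arm is possible but not shown. The 30-day SAE rate is not affected, on the assumption that the Section 17.2 exemption also governs how that rate is counted. The conclusion further assumes that routine inpatient care, which the plan does not describe in this respect, does not already provide a liver panel for every patient. If it does, the plan need only say so and name the time points.

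This is a modest, inexpensive improvement in ascertainment and not a flaw in the primary analysis.

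**What to change.** Reconcile the Section 10.0 schedule with Section 17.2:

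- Add alkaline phosphatase, ALT, AST and bilirubin to the blood draws already scheduled on Day 1 and at 10-14 days, in the table and in the text.
- State whether those two draws, and the 2-week period in Section 17.2, run from each embolization session or only from completed treatment. Section 9.0 counts two sessions as one treatment. State also whether the extra two-session visit comes before or after the second session.
- Tabulate the worst CTCAE grade for each test by arm over the 2 weeks, with the number of patients tested as the denominator.
- Check the placement of the liver-test marks in the table against Section 8.0.

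If the tests are not added, Section 17.2 should at least say that only rises found on clinically ordered tests are captured, and the toxicity report should carry that limitation.

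The cost is two sets of four assays per treatment (per session if the draws follow each session), possibly an extra tube at the same draw, and collection of local laboratory reports for the 10-14 day sample. No new visit is needed where the draw is already scheduled, and no change to patient management is implied.

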## 18.0 INFORMED CONSENT PROCEDURES

Before protocol-specified procedures are carried out, consenting professionals will explain full details of the protocol and study procedures as well as the risks involved to participants prior to their inclusion in the study. Participants will also be informed that they are free to withdraw from the study at any time. All participants must sign an IRB/PB-approved consent form indicating their consent to participate. This consent form meets the requirements of the Code of Federal Regulations and the Institutional Review Board/Privacy Board of this Center. The consent form will include the following:

1. The nature and objectives, potential risks and benefits of the intended study.
2. The length of study and the likely follow-up required.
3. Alternatives to the proposed study. (This will include available standard and investigational therapies. In addition, patients will be offered an option of supportive care for therapeutic studies.)
4. The name of the investigator(s) responsible for the protocol.
5. The right of the participant to accept or refuse study interventions/interactions and to withdraw from participation at any time.

Before any protocol-specific procedures can be carried out, the consenting professional will fully explain the aspects of patient privacy concerning research specific information. In addition to signing the IRB Informed Consent, all patients must agree to the Research Authorization component of the informed consent form.

Each participant and consenting professional will sign the consent form. The participant must receive a copy of the signed informed consent form.

## 20.0 APPENDICES

### Appendix 1. ECOG Performance Status Criteria.

Grade	ECOG
0	Fully active, able to carry on all pre-disease performance without restriction
1	Restricted in physically strenuous activity but ambulatory and able to carry out work of a light or sedentary nature, e.g., light house work, office work
2	Ambulatory and capable of all self care but unable to carry out any work activities. Up and about more than 50% of waking hours
3	Capable of only limited self care, confined to bed or chair more than 50% of waking hours
4	Completely disabled. Cannot carry on any self care. Totally confined to bed or chair
5	Dead

### Appendix 2. Diagnostic Criteria for HCC

#### EASL Diagnostic Criteria for HCC

Cytology-histological criteria.

- Non-invasive criteria (restricted to cirrhotic patients)
  1. Radiological criteria: Two coincident imaging techniques\*
    - Focal lesion > 2cm with arterial hyper vascularization
  2. Combined criteria: One imaging technique associated with AFP
    - Focal lesion > 2 cm with arterial hyper vascularization
    - AFP levels > 400 ng/mL

\*Four techniques considered: US, Spiral CT, MRI and angiography

### Appendix 3. Okuda Staging

Tumor size >50%	“+”
Ascites clinically detectable	“+”
Albumin <3 g/dl	“+”
Bilirubin > 3	“+”
Stage I	no positive indicators
Stage II	1-2 positive indicators
Stage III	3-4 positive indicators
